Main Inclusion Criteria	Adult patients undergoing general anaesthesia for relevant procedures during the pre-defined study window (as defined by this study, see Section 7) within hospitals affiliated with the Pan-London Perioperative Audit and Research Network (PLAN) and other regional trainee networks
Data collected/storage (if applicable)	Anonymised data will be stored on the PLAN REDCap secure data capture server.

4 Introduction

Although most airway management is uncomplicated, when complications occur they can be catastrophic resulting in significant morbidity and mortality [1]. The severe acute respiratory syndrome coronavirus-2 (SARS-CoV-2) pandemic has resulted in significant changes to airway management [2] due to concern over transmission of aerosolised virus particles to healthcare professionals [3]. Initial reports suggest that patients infected with SARS-CoV-2 may be more at risk of airway complications including hypoxaemia [4], airway trauma [5], and airway oedema [6]. While it is possible SARS-CoV-2 itself may be a risk factor for airway complications, aerosol precautions, designed to reduce the transmission of virus particles to healthcare workers, may also contribute. These aerosol precautions include modified anaesthetic techniques, unfamiliar equipment, and personal protective equipment (PPE).

Anaesthetic management varies, in part, depending on the patient's coronavirus disease 2019 (COVID-19) status. Personal protective equipment for droplet precautions is advised for staff dealing with COVID-19 negative patients and comprises eye protection, gloves, and surgical facemasks at the minimum [7]. COVID-19 positive or COVID-19 unknown patients require staff to use a greater level of aerosol precaution PPE, comprising respirator masks (e.g. FFP3), long-sleeved gowns, gloves and eye protection. It is currently not known whether use of aerosol precaution PPE and other methods used to reduce viral transmission during airway interventions increases the risk of airway complications, but it may be a contributing factor to difficult intubations reported in COVID-19 patients [6, 8].

We aim to describe airway management and the different components of the bundle of aerosol precautions used to protect healthcare workers, and report the associated incidence of airway complications.

5 Trial objectives and purpose

Aims

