6.1 Study Design

AeroComp is service evaluation exploring the incidence of airway complications amongst patients undergoing general anaesthesia for surgical procedures within NHS Trusts. All adult patients undergoing any surgical procedure (with the exception of obstetric procedures) with the primary method of anaesthesia planned to be general anaesthesia will be eligible for enrolment to this study. The study duration will encompass 5 days (patients being enrolled over a 96 hour consecutive window with a further day of follow-up data collection) with an estimated total of 3600 patients being included. Individual sites are free to choose their own data collection window between 1st November

2021 and 3rd December 2021 as long as the 96 hour window commences at 07:30 on a Monday and closes at 07:29 on a Friday.

Primary outcome:

 Incidence of airway complications at both induction and emergence, defined as a composite of: airway trauma, aspiration, dental/lip/mucosal injury, change of intubation device, desaturation, three or more laryngoscopy attempts, grade 3 or 4 laryngoscopy, difficult face mask ventilation, difficult supraglottic airway device (SAD) usage, emergency front-of-neck airway, failed tracheal intubation, laryngospasm, oesophageal intubation (immediate or delayed recognition), requirement of reintubation immediately after extubation, and need for second intubator.

Secondary outcomes:

- Risk of composite outcome of airway complications will be reported for each individual component of the aerosol precaution bundle.
- Individual complications that comprise the primary outcome.
- Subjective operator assessment of airway difficulty
- Unanticipated airway difficulties necessitating significant deviation from the original airway plan.
- Composite risk of airway complication and association with confirmed/suspected COVID-19 infection, known negative COVID-19 infection without any potential COVID-19 risks, and all other patients.

7 List selection

Operating lists from all participating NHS hospitals will be included, with patients from those lists being eligible. Both elective and emergency cases will be included. The centres and local investigators will be identified by the Pan-London Perioperative Audit and Research Network (PLAN) or other national trainee research networks.

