Shaw *et al.* [12] reported an incidence of 91 airway complications in 1874 patients (~5%). Therefore, assuming an anticipated 5% incidence of our primary outcome in our study population, a desired error of +/-1% (absolute error) of our estimate for the incidence, and a 95% confidence level of achieving the desired estimate precision, we calculate the sample size required for our study to be \geq 1822 patients (Appendix 4; [13]). For a conservative estimate, with 50 centres each performing 18 procedures a day, we expect 3600 patients to be included, allowing acceptable rates of detection of rare events.

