10.2 Statistical analysis

Incidence of airway complications amongst the sampled population will be reported as a composite of airway complications as mentioned in **Section 9**.

Continuous data will be reported using means (standard deviation, SD) or medians (interquartile ranges [range]) where appropriate. Categorical data will be reported as numbers (percentages, %) with 95% confidence intervals (CI) calculated using an appropriate method, where applicable. A p value of < 0.05 will be considered as statistically significant. Relationships between categorical variables and outcome measures will be presented as univariate odds ratios with accompanying p-values (Pearson's Chi-square test with Yates' continuity correction). Univariable logistic regression models will be fitted to investigate potential associations between variables describing patient, operator or procedural characteristics and the primary outcome of incidence of airway complications. A multivariable logistic regression model will then be fitted to include all covariates to obtain adjusted association estimates. Variables included in the regression modelling will be selected based on scientific and clinical plausibility of affecting the outcome of airway management.

11 Ethical considerations

This study is designed as a service evaluation, and no ethical approval is expected to be required. As we are collecting routinely captured data with no patient identifiable data, and will not involve either direct patient contact or influence their care in any way, no patient consent will be required. Approval from the Caldicott Guardian at the lead site (Guy's and St. Thomas' NHS Foundation Trust, London, UK), and audit registration at all recruiting centres will be required prior to commencing the project. Participating hospitals will ensure that their local investigators will be appropriately trained, but no GCP certification will be required from investigating teams as this is a service evaluation. The local PI will ensure that no patient identifiable information will be stored during the study.

12 Financing and Insurance

No funding will be required for this study. All investigators will be NHS employees working in their respective trusts and standard NHS Indemnity will apply.

13 Reporting and dissemination

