15.4 Appendix 4 – Sample Size Calculation

Sample Size for Frequency in a Population

Population size(for finite population correction factor or fpc)(N):	1000000
Hypothesized % frequency of outcome factor in the population (p):	5%+/-1
Confidence limits as % of 100(absolute +/- %)(d):	1%
Design effect (for cluster surveys-DEFF):	1

Sample Size(n) for Various Confidence Levels

Confidence	Level(%)	Sample Size
95%		1822
80%		780
90%		1284
97%		2232
99%		3142
99.9%		5117
99.99%		7142

Equation

Sample size *n* = [DEFF*Np(1-p)]/ [(d²/Z²_{1-q/2}*(N-1)+p*(1-p)]

where

n = sample size

DEFF = design effect from clustered data

N = population size (assumed to be 1 million)

p = the estimated proportion

d = the desired absolute precision

 $1-\alpha$ = the desired confidence level

Z = the Z-score for the corresponding confidence level (normally 1.96 for a 95% confidence level)

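### The only adjusted COVID-19 odds ratio most naturally comes from a model that also holds the aerosol precautions, so no confounder-adjusted overall COVID-19 association is planned

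*Protocol*

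**What the plan says.** Protocol Section 10.2 plans three layers of association analysis:

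- univariate odds ratios with chi-square p-values for categorical variables;
- univariable logistic models for features of the patient, the operator and the procedure;
- one adjusted analysis: "A multivariable logistic regression model will then be fitted to include all covariates to obtain adjusted association estimates".

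The only selection rule is that a variable could plausibly influence airway outcome. No covariate list is given, and nothing separates confounders from variables on the causal path. The threshold is stated as "A p value of < 0.05 will be considered as statistically significant".

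Two exposure questions are declared. Aim 2 in Section 5 and the secondary outcomes in Section 6.1 ask about each component of the precaution bundle. Section 6.1 also lists "Composite risk of airway complication and association with confirmed/suspected COVID-19 infection", compared with a known-negative group and all other patients.

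Section 4 links the two exposures: "COVID-19 positive or COVID-19 unknown patients require staff to use a greater level of aerosol precaution PPE". It adds that anaesthetic management depends partly on status, and that both the virus and the precautions could contribute to complications.

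**The concern.** On the protocol's own account, COVID-19 status comes first, precautions follow from it, and precautions may affect complications. Status is therefore a confounder for the precaution question, while precautions are mediators for the COVID-19 question. A single set of coefficients cannot give the overall association for both exposures.

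For the precaution question, a model holding status and precautions together is reasonable. For the COVID-19 question, it removes whatever part of the association runs through PPE and technique. What is left is at most a direct effect, yet Section 10.2 would present it simply as the adjusted association.

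At stake is how one secondary outcome is read. The study would have a crude COVID-19 odds ratio, mixed with case-mix differences, and an adjusted one with the precaution pathway removed. Neither is the overall association adjusted for case mix. If the two differ, a reader cannot tell whether confounding or mediation explains the gap.

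**Working it through.** **The plan's own figures.** The Appendix 4 formula with N = 1,000,000, p = 0.05, d = 0.01, Z = 1.96 and design effect 1 gives 1821.4, that is 1822 as stated. Expected recruitment is 50 × 18 × 4 = 3600. These concern the precision of the incidence and are not disputed; 3600 is used below.

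**Assumed inputs (not in the documents).** Risk without aerosol PPE is 4.5%, near the protocol's anticipated 5%. PPE is used in 90% of patients in the COVID-19 group and 10% of the others. The PPE odds ratio is 2. Two status groups are used for simplicity, with no confounders, so here the unadjusted odds ratio equals the total one.

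**Step 1: effect wholly through PPE.**
- Odds without PPE: 0.045/0.955 = 0.0471. With PPE: 0.0942, a risk of 0.0861.
- COVID-19 group: 0.1 × 0.045 + 0.9 × 0.0861 = 0.0820.
- Other patients: 0.9 × 0.045 + 0.1 × 0.0861 = 0.0491.
- Total odds ratio: (0.0820/0.9180)/(0.0491/0.9509) = 1.73.
- Within each PPE level the two groups have the same risk, so the PPE-adjusted odds ratio is 1.00.

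**Step 2: a direct odds ratio of 1.5 added.**
- COVID-19 group without PPE: odds 0.0707, risk 0.0660. With PPE: odds 0.1414, risk 0.1239.
- Risk: 0.1 × 0.0660 + 0.9 × 0.1239 = 0.1181.
- Total odds ratio: (0.1181/0.8819)/(0.0491/0.9509) = 2.59. The PPE-adjusted odds ratio is 1.50.

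**Step 3: sensitivity, no direct effect.**

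| PPE use, COVID-19 v other | PPE odds ratio | Total odds ratio | Adjusted |
|---|---|---|---|
| 70% v 30% | 1.5 | 1.17 | 1.00 |
| 70% v 20% | 2 | 1.42 | 1.00 |
| 90% v 10% | 2 | 1.73 | 1.00 |
| 90% v 10% | 2.5 | 2.05 | 1.00 |
| 90% v 10% | 3 | 2.35 | 1.00 |

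**Step 4: precision.** With 3600 patients and the Step 1 inputs, the standard error of the COVID-19 log odds ratio rises when PPE is added: from 0.28 to 0.33 with 5% in the COVID-19 group, 0.21 to 0.26 with 10%, and 0.14 to 0.22 with 30%.

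**Step 5: simulation** (3600 patients, 500 replicates, PPE use 90% v 20%, PPE odds ratio 2).
- 10% positive, no direct effect: median odds ratio 1.55 unadjusted (55% of replicates with p < 0.05) and 0.99 adjusted (5%).
- 5% positive, direct odds ratio 1.5: 2.33 unadjusted (90%) and 1.46 adjusted (34%).

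**The case against.** Several points on the other side carry weight.

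- **The crude result stays visible.** A reader might infer that the study would report no COVID-19 association when risk is plainly higher. Section 10.2 does not support that: status is categorical, so its univariate odds ratio is reported. In the example above, 1.73 would appear beside 1.00. What remains is that the crude figure is open to confounding and no case-mix-adjusted counterpart is planned.
- **Joint entry is inferred.** No covariates are listed, PPE is not named in the regression text, and an analysis plan that is not shown may settle the sets. This limits confidence. Still, the protocol fixes a single all-covariate model and a selection rule that, given Sections 4 to 6, would admit status and precautions together.
- **The wording is descriptive.** Group risks and univariate odds ratios would satisfy a literal reading of the secondary outcome. But Section 10.2 itself commits to adjusted estimates, so it matters what the adjusted one means.
- **The conditional coefficient is useful.** Section 4 asks whether the virus itself adds risk beyond the precautions, and holding precautions equal addresses that. A reader might conclude that the all-covariate model is wrong and should go. It is not wrong; its COVID-19 coefficient needs a label.
- **The null is built in.** Exactly 1.00 follows from assuming full mediation. With any direct effect in the same direction the result is attenuation, and Section 4 says management depends on status only in part.

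**Conclusion.** The point holds in a limited form. If status and precautions enter one model, as the text most naturally implies, the adjusted COVID-19 odds ratio is conditional on precautions and is not the overall association. No other adjusted COVID-19 estimate is planned.

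In the no-direct-effect scenarios tabulated, total odds ratios of 1.17 to 2.35 all become 1.00. With a direct odds ratio of 1.5, 2.59 becomes 1.50. PPE uptake, PPE effect and the share of patients in the COVID-19 group are assumptions throughout, and the two-group comparison simplifies the protocol's three. The documents give no figures on how urgency or ASA differ by status, so the confounding in the crude odds ratio cannot be sized.

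The precaution analysis, the primary incidence estimate and the sample size are not affected. This is a worthwhile correction to one secondary outcome, not a flaw in the study's main result.

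**What to change.** In Section 10.2:

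1. Add one logistic model for the COVID-19 secondary outcome, using the three status groups of Section 6.1. Adjust for age, sex, BMI, ASA, urgency, specialty, severity, time of day and location. Leave out PPE, technique and equipment.
2. Keep the all-covariate model, with status and the precaution components entered together, for the precaution question. Separate models for single components are not a substitute: Section 4 describes PPE items used as a set, so one item would be credited with another's effect.
3. State that the COVID-19 coefficient in the all-covariate model is conditional on precautions.

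Active infection may itself partly change ASA and urgency, so show the new model with and without those two variables. The cost is a few sentences and one further model, plus its sensitivity version, on data already collected under Section 9.1.

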15.1 Appendix 1 - Protocol amendment / Revision history

Version Stage	Version No.	Version Date	Protocol updated & finalised by	Appendix No. Detail the reason(s) for the protocol update
	1.0	17/09/2021	[name] [name] [name] [name] [name] [name] [name] [name] [name] [name]	Subject to Final Approval
	1.1	30/09/2021	[name] [name] [name] [name] [name] [name] [name] [name] [name] [name]	Changed layout of CRFs Split airway device usage into awake/asleep Defined surgical urgency Added non-binary sex option
Current	1.2	13/10/2021	[name] [name] [name] [name] [name] [name] [name] [name] [name] [name]	Removed Research Questions section as this is a service evaluation, not research. Reworded use of local ID to make it explicit this is removed prior to storage of CRFs. Add section to Data Handling describing anonymised data.

15.2 Appendix 2 – Sample Case Record Form (CRF)

AER	COMP	Study Day ¹ : D Monda	, ,	Study ID: Hospital	:	
PATIENT DETAILS		PATIENT COVID-19 STATUS		SURGICAL DETAILS		
Age: 18 to 60 to Sex: Male Fema Other	79 🗖 80 and over	 Positive (PCR/LFT positive; CC Negative (PCR/LFT negative a COVID-19 free pathway) 	WID-19 symptoms; recent exposure) nd self-isolated and cohorted in	Surgical urgency ² :	Severity ³ : D Mind D Inter D Majo	rmediate
ASA Score:	− 29.9 □ 30.0 − 34.9	Unclear (No test result availal isolated; not cohorted in COVID-		Specialty: Breast ENT Bariatric General Cardiac Gynaecology Cardiology Max-Fax Dental Neurosurgery Other:	 Ophthalmology Ortho/Trauma Plastics Radiology Thoracic 	TransplantUrologyVascular
ANAESTHETIC DETA				Procedure performed within main operating theat	re complex: D Yes	No
Start time ^{1,4} : Grade of initial airway manager ⁵ : PPE worn by anaest Eye protection:	 00:00 to 07:29 07:30 tilde CT1-2 ST5-7 Consultion CT/ST3-4 SAS/SCF Other Other 07:30 tilde 07:30 ti	Itant Grade of second her airway manager ^{5,6} :	5 B	AIRWAY COMPLICATIONS (tick all that apply) Tracheal intubation attempts ⁸ : 1 2 Best grade of laryngoscopy ⁸ : 1 2 Was the patient woken up at the end of surgery? ⁹	□ 3 □ >3 □ 2b □ 3 □ Yes □ No	□ 4
Respiratory	 Other Surgical face mask 		Hazmat suitOther	Airway complications: (tick all that apply)	Induction	Emergence ⁹
rotection:	 Disposable FFP2/3 respirator Re-usable FFP2/3 respirator Powered air purifying respira Other 		 Single pair of gloves Double pair of gloves Other 	Airway trauma Aspiration Change of intubation device Death ¹⁰		
IRWAY MANAGEN Induction:	MENT (tick all that apply) Inhalational Intravenous: non-RSI	Equipment:	Bougie Stylet Cofeed pillour	Dental injury Desaturation (SpO₂ ≤90%) Desaturation (SpO₂ ≤80%) Difficult mask ventilation (2-person technique)		
Dxygenation:	 Intravenous: RSI/modified RS Pre-oxygenation Post-induction mask ventilati Apnoeic oxygenation 	ion	 Oxford pillow High-flow nasal cannulae Low-flow nasal cannulae Clear plastic 'aerosol' box Other 	Difficult SAD (excessive leak, poor ventilation, hypo Emergency front-of-neck airway Failed tracheal intubation – continue with SAD		
Airway device:	 Face mask (as sole airway de Supraglottic airway device Tracheal tube Other⁷ 	Airway technique: Direct laryngoscopy Video laryngoscopy Flexible bronchosco		Failed tracheal intubation – awaken patient Laryngospasm not reversed with positive pressure Lip/mucosal injury	D	
Was cricoid force us		vay plan?	□ No □ No	Oesophageal intubation (recognised) ¹¹ Oesophageal intubation (delayed recognition) ¹¹ Reintubation immediately post-procedure ⁹		
Subjective ease of fa Subjective ease of S Subjective ease of tr		tempted 🗖 1 (Easy) 🗖 2	3 4 5 (Difficult) 3 4 5 (Difficult) 3 4 5 (Difficult) 5 5 (Difficult)	Second airway manager required ⁶ AeroComp Case Record Form v1.2		

AeroComp Case Record Form v1.2 Notes

- 1) The study day is defined as the time period from 07:30 on the specified day until 07:29 the following morning. Thus, if an operation commences at 04:00 on Friday morning, the "Study Day" should be Thursday, and Start Time should be 00:00 to 07:29.
- 2) Surgical urgency is defined as per NCEPOD (https://www.ncepod.org.uk/classification.html)
 - a. Immediate Immediate life, limb or organ-saving intervention resuscitation simultaneous with intervention. Normally within minutes of decision to operate.
 - b. Urgent Intervention for acute onset or clinical deterioration of potentially life-threatening conditions, for those conditions that may threaten the survival of limb or organ, for fixation of many fractures and for relief of pain or other distressing symptoms. Normally within hours of decision to operate.
 - c. Expedited Patient requiring early treatment where the condition is not an immediate threat to life, limb or organ survival. Normally within days of decision to operate.
 - d. Elective Intervention planned or booked in advance of routine admission to hospital. Timing to suit patient, hospital and staff.
- 3) Surgical severity is defined as per NICE guidance NG45 (https://www.nice.org.uk/guidance/ng45/chapter/recommendations). Examples include:
 - a. Minor Excising skin lesion, draining breast abscess.
 - b. Intermediate Primary repair of inguinal hernia, excising varicose veins in the leg, tonsillectomy or adenotonsillectomy, knee arthroscopy.
 - c. Major Total abdominal hysterectomy, endoscopic resection of prostate, lumbar discectomy, thyroidectomy, total joint replacement, lung operations, colonic resection, radical neck dissection.
- 4) Start time should be the time of the first set of observations upon the anaesthetic record.
- 5) SAS specialty and associate specialist; SCF senior clinical fellow. If no exact match is presented please choose the closest equivalent grade.
- 6) Second airway manager: if a second individual took over management of the airway following management by the initial airway manager their grade should be recorded here and "second airway manager required" ticked within the complication section. Leave blank if not applicable.
- 7) Other: this applies to, for example, rigid bronchoscopes, jet ventilators and transnasal humidified rapid-insufflation ventilatory exchange. This should be ticked only if it was the primary airway device following induction of anaesthesia. Typically this will be a planned technique involving pre- +/- per-oxygenation following discussion with the operating surgeon beforehand. Also select if the primary means of oxygenation during the procedure is via a surgically placed jet ventilator (e.g. laryngeal procedures) and no other airway device is placed prior or subsequently by the anaesthetist. The exact device used does not have to be specified.
- 8) Tracheal intubation attempts/laryngoscopy grade should be left blank if intubation is not attempted. The grade here refers to the Cormack and Lehane system as modified by Yentis and Lee, shown below.
- 9) If the patient was not woken up at the end of surgery, emergence complications should not be recorded. If the patient was woken up and then immediately reintubated, this should be recorded as: Woken up: Yes; Reintubation immediately post-procedure: On emergence.
- 10) Only death due to hypoxia or another complication of airway management should be recorded.
- 11) Recognised oesophageal intubation is detected after the first but before the fourth ventilatory breath has been delivered. Delayed recognition is when four or more ventilatory breaths have been delivered.

	1	2		3	
Original Cormack and Lehane system	Full view of the glottis	Partial view of the glottis or arytenoids		Only epiglottis visible	Neither glottis nor epiglottis visible
View at laryngoscopy	E	Y	Y		
Modified system	1 As for original Cormack and Lehane above	2a Partial view of the glottis	2b Arytenoids or posterior part of the vocal cords only just visible	3 As for original Cormack and Lehane above	4 As for original Cormack and Lehane above

E = epiglottis, LI = laryngeal inlet. From Yentis SM, Lee DJH. (1998) Grading of direct laryngoscopy. Anesthesia. 53:1041-4.

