9.1 Data to be collected

Data will be collected on all operating lists with patients who meet inclusion criteria in participating hospitals. Each hospital taking part will have nominated staff who will be responsible for data collection.

For each day of the study the local investigating team will determine the total number of patients eligible for inclusion.

For each included patient, the anaesthetist or anaesthetic assistant (e.g. operating department practitioner, anaesthetic nurse) will be asked to complete a paper case record form (CRF; *Appendix* 2). Where more than one anaesthetist is involved, the most senior anaesthetist should be asked to complete the CRF.

Completed CRFs will be collected from the treating anaesthetic team. Local investigators will be responsible for ensuring accuracy and completeness of data. Where appropriate, this should include cross-checking with patient notes and other sources of information.

Completed CRFs will be stored in a secure location accessible by the local PI and other named members of the study team in accordance with NHS Information Governance standards. Information from each paper CRF, as well as the total number of eligible patients for each day of the project, will be entered via a secure web-based portal onto a secure database. The database will have data validation rules built-in to ensure accurate data entry (e.g. range checks, and field validation).

No patient-identifiable information will be uploaded to the secure database. Each site may elect to use a local ID upon the CRF to facilitate retrospective data capture within the immediate time frame of the project however this should be detached once the CRF is completed and will not form part of the dataset uploaded to the data capture server. Paper CRFs will be retained by the local study team in a locked, secure location in the hospital for a period of 6 months after the project ends to allow queries about study quality to be addressed during data cleaning and analysis. The local ID will not remain upon the CRF during this period.

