 - Airway devices utilised: facemask, supraglottic airway device; tracheal tube; other (including rigid bronchoscope, jet ventilator and transnasal humidified rapid-insufflation ventilatory exchange)
 - Airway techniques including: direct laryngoscopy; videolaryngoscopy; use of a flexible bronchoscope over which a tracheal tube is passed, categorised into whether performed awake or asleep
 - Use of cricoid force?

- Adjunct equipment including: bougie; stylet; Oxford or HELP pillow; high and lowflow nasal cannulae; aerosol boxes or drapes; as well as a free text option for other potential equipment

- Patient COVID-19 status:
 - Positive: RT-PCR or lateral flow test positive for SARS-CoV-2; OR symptoms consistent with COVID-19 with no SARS-CoV-2 test available; OR recent exposure to SARS-CoV-2
 - Negative: RT-PCR or lateral flow test negative for SARS-CoV-2 infection; AND actively cohorted with other COVID-19 negative patients for the entirety of their hospital stay prior to this operation; AND self-isolated according to institutional guidelines.
 - Unclear: No SARS-CoV-2 result available with no risk factors; OR not self-isolated according to institutional guidelines; OR not in a COVID-19-free pathway.
- Whether anaesthesia was terminated at the end of the procedure with a plan to wake up the patient (emergence from anaesthesia).

Airway complications:

- Number of tracheal intubation attempts.
 An attempt is defined by the number of times the laryngoscopy device is inserted or reinserted into the patient's airway.
- Best grade of laryngoscopy: modified Cormack and Lehane grading [9] into 1, 2a, 2b, 3 and 4.
- The following complications categorised into induction and emergence (defined as the period around the time of cessation of anaesthesia until hand over of patient to recovery/intensive care staff):
 - Airway trauma: evidence of airway bleeding or oedema.
 - Dental injury (arising solely from anaesthetic, rather than surgical, interventions)
 - Lip and mucosal injuries (arising solely from anaesthetic, rather than surgical, interventions)
 - Pulmonary aspiration: inhalation of oropharyngeal or gastric contents into the larynx and lower respiratory tract [10]
 - Change of intubation device: use of an additional airway device, e.g. change from supraglottic airway to tracheal tube, change from direct to videolaryngoscopy (or vice versa), use of bougie if not initially anticipated, change in type of laryngoscope e.g. McCoy vs Macintosh blade

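### The CRF complication grid has no entry for no complication, so a skipped grid or emergence column cannot be told from an event-free case and the primary incidence may be under-ascertained

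*Protocol*

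**What the plan says.** The primary outcome (Section 6.1) is the incidence of a composite of airway complications at induction and emergence. Section 9.1 introduces most components with "The following complications categorised into induction and emergence". The sample form in Appendix 2 prints them as a grid with those two columns, in the section headed "AIRWAY COMPLICATIONS (tick all that apply"; the same instruction is repeated above the grid. The readable rows run from airway trauma to the need for a second airway manager. No row or box for no complication appears among them, and the Section 9.1 list has none either.

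Three items in the same section lie outside the grid:
- number of intubation attempts and best laryngoscopy grade, for which note 8 says "Tracheal intubation attempts/laryngoscopy grade should be left blank if intubation is not attempted";
- the yes/no item "Was the patient woken up at the end of surgery".

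Note 9 adds: "If the patient was not woken up at the end of surgery, emergence complications should not be recorded".

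On data quality, Section 9.1 says "Local investigators will be responsible for ensuring accuracy and completeness of data", then "Where appropriate, this should include cross-checking with patient notes and other sources of information". It also says "The database will have data validation rules built-in to ensure accurate data entry (e.g. range checks, and field validation". The local ID is to be detached once the form is complete, and the forms are kept for six months for queries. The protocol does not say how an empty grid is to be coded.

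**The concern.** A tick-only list records events but not the statement that none occurred. An empty grid can mean that nothing happened or that nobody answered. The emergence column has the same problem by itself: a patient marked as woken with nothing ticked at emergence may have had an uneventful emergence, or the form may have been filled in after induction and not reopened.

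At stake is the primary estimate. If unanswered grids are read as event-free, the error runs in one direction, a larger sample does not reduce it, and the confidence interval does not show it. If skipping also differed by urgency, PPE or site, the associations in the second aim would be affected too. The protocol gives no information on whether it would.

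**Working it through.** **1. The plan's own figures.** Inputs from Section 10.1 and Appendix 4: p = 0.05, d = 0.01, Z = 1.96, N = 1,000,000, design effect 1.

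n = N p(1−p) / [(d²/Z²)(N−1) + p(1−p)] = 47,500 / (26.03 + 0.0475) = 1821.4, rounded up to 1822. This reproduces the stated figure. Expected enrolment is 50 × 18 × 4 = 3600, also as stated. The 95% half-width at 5% is 1.00 point with 1822 patients, and 1.96 × √(0.05 × 0.95 / 3600) = 0.71 points with 3600.

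**2. How a blank would have to be read.** At 5% incidence, 3600 × 0.05 = 180 patients have an event and 3420 (95%) do not. Correct forms for those 3420 have an empty grid. Setting every empty grid to missing would remove nearly all non-events from the denominator. With this form, reading blank as no event is the only workable rule.

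**3. What the stated checks can catch.**

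| What was skipped | Visible on the form? |
|---|---|
| Whole complication section | Yes: the woken-up item is blank, and no note permits that |
| Grid only, upper items filled | Not from the grid; other fields may prompt a query in some cases |
| Emergence column only, patient woken | Not from the column |
| Emergence column, patient not woken | Correctly blank under note 9 |

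Attempts and grade may be blank in patients not intubated, so they give no signal there.

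**4. Size, if skipped grids are counted as no event.** The documents give no skip rate, so m is an assumption. With skipped cases at average risk, the loss is at most p × m:

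| m (assumed) | Largest loss at p = 5% | Reported incidence, at lowest |
|---|---|---|
| 1% | 0.05 points | 4.95% |
| 2% | 0.10 points | 4.90% |
| 5% | 0.25 points | 4.75% |
| 10% | 0.50 points | 4.50% |
| 20% | 1.00 point | 4.00% |

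This is an upper bound at average risk for two reasons. At least three attempts and a grade 3 or 4 view count towards the composite and are recorded outside the grid. If only the emergence column is skipped, only patients whose sole event was at emergence are lost.

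For comparison, p × m reaches the planned 1-point margin at m = 0.01/0.05 = 20%, and the 0.71-point half-width at m = 0.0071/0.05 ≈ 14%.

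**5. If skipped cases are not at average risk.** With k the risk of skipped relative to completed cases (assumed) and overall risk held at 5%, the reported incidence is p − m k p / [(1−m) + m k], again taking every event in a skipped form as lost:
- m = 5%: 4.87% for k = 0.5, 4.52% for k = 2;
- m = 10%: 4.74% for k = 0.5, 4.09% for k = 2.

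**The case against.** The strongest reply is that no rule in the protocol codes an empty grid as zero and no skip rate is given. Handling of blanks may sit in the REDCap build or an analysis plan, and Appendix 2 is only a sample paper form. A reader might infer from the form that skipped sections are counted as zero and that the incidence is biased. The documents do not support that as fact; they support a risk.

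A reader might also infer that completeness checks can find nothing. That is too strong:
- the woken-up item exposes a wholly skipped section;
- attempts and grade do the same in intubated patients;
- note 6 requires the grade of a second airway manager to be matched by a tick in the grid;
- the item on deviation from the airway plan and the ease scores can prompt a query in a difficult case;
- the validation rules named are examples, not a full list.

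Nor can it be said that emergence is the likelier half to be missed. The protocol offers no evidence, although its emergence window runs to handover and reintubation counts for 30 minutes after the procedure.

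The form is also only partly readable. The row on difficult supraglottic devices is cut short and tick-box cells are lost, so the absence of a box is asserted for the readable text only. The Section 9.1 list supports it.

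What remains is narrower. None of these checks reliably detects a form with the upper items filled and the grid or emergence column left blank. Cross-checking against notes is conditional, and the stored form no longer carries the local ID. A required field in REDCap alone would not help, because whoever transcribes the paper form sees the same blank. A later analysis rule cannot recover an answer that was never collected.

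**Conclusion.** The point holds as a risk of under-ascertainment of the primary composite, in one direction and of unknown size. It arises where the grid or its emergence column is skipped and the rest of the form is filled in. At 5% incidence and average risk the loss is at most 0.05 to 0.10 points with 1–2% skipped, 0.25 points with 5%, and 1.0 point with 20%. All these skip rates are assumptions, and the bound would be exceeded if skipped cases carried higher risk.

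A reader might double these losses by taking a 10% incidence and set them against the ±1-point margin. That margin was planned at 5%, and the protocol gives no basis for 10%. The required sample size of 1822 is unaffected. The change is worth making because the omission cannot be repaired after collection and the remedy is cheap.

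**What to change.** - **Paper form:** add a box for no airway complication under induction and another under emergence.
- **REDCap:** make a yes/no field for any complication mandatory for induction in all patients, and for emergence only when the woken-up item is yes. Code emergence as not applicable in patients not woken, in line with note 9. A blanket rule that no tick means missing would misclassify them.
- **Queries:** where an applicable phase has neither a complication nor the new box ticked, check it against the notes before the local ID is detached. If it stays unresolved, treat that phase as missing, not as event-free.
- **Reporting:** give the number of unresolved phases alongside the incidence.

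The cost is one extra tick per phase, the mandatory e-CRF field for each phase, and a new form version issued before collection opens.
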